17. NUMBER OF INVESTIGATIONAL SITES

The trial will be performed at two sites with multiple practitioners.

Consideration was given to using a single vs. multiple sites as well as multiple practitioners. Practically, we found a learning curve in our pilot study in which proficiency (measured as deployment time < 3minutes in simple diagnostic procedures) stabilized after about n= 2-3 per practitioner. Given n= 90 for the study with all cases consisting of more complex interventional procedures, if the total number of practitioners were 6 (e.g. 2 hospitals*3 practitioners/hospital), for example, then each physician would do 15 cases, or about 5 times the number it takes to become proficient. We decided that two sites with multiple practitioners would satisfy the requirement to minimize bias without introducing excessive start-up variation.

18. METHODS / STUDY DESIGN

Institutional Review Board (IRB) approval will first be obtained. A subject's participation is a one-time event (plus follow-up) that occurs after obtaining informed consent. The subjects will not incur any costs associated with the study procedures.

At the catheter lab site, subjects will be screened through a standard of care history. After determining that the patient qualifies for enrollment into the study, an investigator or delegated study personnel will obtain an informed consent. After the patient's informed consent is obtained, study personnel will interview the subject and document subject data, including their age, gender, race, and patient history into their file. The subject source data is then recorded on a sponsor-provided Case Report Form (CRF).

Each subject will undergo the doctor-determined interventional procedure before closing with SiteSeal™.

The first 50 patients will receive a pre-device deployment ultrasound of the access site on the day of catheterization and a post-procedure ultrasound (after device removal and no later than the 30day follow-up) to detect silent complications, including vascular injury requiring repair, pseudoaneurysms requiring thrombin or fibrin adhesive injections, or bleeding requiring transfusions.

All patients will return for a follow-up visit at 30 days (± 1 week) post-procedure. A physician investigator (i.e. principal investigator, sub-investigators, physician assistants and/or nurse practitioners associated with the investigators) will examine the femoral artery access site. Any access site-related complications will be reported to the PI.

19. ANALYSIS OF RESULTS

For each patient, a separate set of Case Report Forms (CRFs) will be completed and comprise the following information:

- Inclusion/exclusion criteria
- Demographics: Age in years, Sex, Race, Height, Weight, BMI.
- Procedure-Related Data
- Medication history
- Previous diagnostic and/or interventional endovascular procedures
- Catheterization procedure data

Primary Endpoints

- Risk for common femoral nerve puncture and common femoral artery laceration (or needle penetration) from blind placement of the Z-stitch.
 - Nerve puncture risk is defined as "the incidence of an involuntary leg muscle contraction and an auditory response at the time of placing the device".

- Common femoral artery laceration (or needle penetration) is defined as "a common femoral artery laceration (or needle penetration) with resultant bleeding or hematoma > 6 cm diameter".

Secondary Endpoints

- Patient Discomfort @ discharge from the catheterization lab and @ 24 hours' post procedure (per phone interview)
 - a. 1-10 scale with 10 being intense pain
- Assessment of complications (major and minor) 30days after leaving the catheterization lab (per visit to physician investigator).

Major complications:

- b. Vascular repair or the need for vascular repair (via surgery, ultrasound-guided compression, trans-catheter embolization, or stent-graft)
- c. Access site-related bleeding requiring transfusion
- d. Any new ipsilateral lower extremity ischemia documented by patient symptoms, physical exam, and/or decreased or absent blood flow on lower extremity angiogram
- e. Surgery or the need for surgery for access site-related nerve injury
- f. Permanent (lasting > 30 days) access site-related nerve injury
- g. Access site-related infection requiring intravenous antibiotics and/or extended hospitalization

Minor Complications

- a. Non-treated pseudoaneurysm documented by ultrasound
- b. Non-treated arteriovenous (AV) fistula documented by ultrasound
- c. Pseudoaneurysm treated with ultrasound-guided thrombin injection or ultrasound-guided fibrin adhesive injection
- d. Access site hematoma greater than 6cm
- e. Access site-related bleeding requiring greater than 30minutes to achieve hemostasis
- f. Late (following hospital discharge) access site-related bleeding
- g. Ipsilateral lower extremity arterial emboli
- h. Transient loss of ipsilateral/contralateral lower extremity pulse
- i. Ipsilateral deep vein thrombosis
- j. Access site-related vessel laceration
- k. Transient access site-related nerve injury
- l. Access site wound dehiscence
- m. Localized access site infection treated with intramuscular or oral antibiotics

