15. OBJECTIVE

Primary: The primary endpoints assess the risk for common femoral nerve damage and common femoral artery laceration from the blind placement of a Z-stitch in the soft tissue above the femoral bundle.

Secondary: The secondary endpoints are to measure patient discomfort (per 24-hour phone interview), and the 30-day incidence of major and 30-day incidence of minor complications (per patient follow-up visit).

Patient Discomfort:

- a. Patient discomfort @ discharge from the catheterization lab:
- b. Patient discomfort @ 24 hours after the procedure:

30day Major Complications:

- a. Vascular repair or the need for vascular repair (via surgery, ultrasound guided compression, transcatheter embolization, or stent graft)
- b. Access site related bleeding requiring transfusion
- c. Any new ipsilateral lower extremity ischemia documented by patient symptoms, physical exam, and/or decreased or absent blood flow on lower extremity angiogram
- d. Surgery or the need for surgery for access site related nerve injury
- e. Permanent (lasting >30 days) access site related nerve injury
- f. Access site related infection requiring intravenous antibiotics and/or extended

hospitalization

30Day Minor Complications:

- a. Non treated pseudoaneurysm documented by ultrasound
- b. Non treated arteriovenous (AV) fistula documented by ultrasound
- c. Pseudoaneurysm treated with ultrasound guided thrombin injection or ultrasound guided fibrin adhesive injection
- d. Access site hematoma greater than or equal to 6 cm
- e. Access site related bleeding requiring greater than 30minutes to achieve hemostasis
- f. Late (following hospital discharge) access site related bleeding
- g. Ipsilateral lower extremity arterial emboli
- h. Transient loss of ipsilateral lower extremity pulse
- i. Ipsilateral deep vein thrombosis
- j. Access site related vessel laceration
- k. Transient access site related nerve injury
- l. Access site wound dehiscence
- m. Localized access site infection treated with intramuscular or oral antibiotics

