26. STATISTICAL PLAN

Objective

The purpose of this study is to establish the safety of the SiteSeal™ Adjunctive Compression Device.

Study Design

The study design is a single arm with 90 enrolled patients, open-label, single center clinical trial.

Handling Missing Data

No imputation will be done for missing data.

Handling Dropouts

The numbers of patients who enter and complete the trial will be tabulated, and details concerning reasons for withdrawals will be listed.

Statistical Methods

Primary Safety Analyses

For the risk of each of the two primary safety endpoints, namely common femoral nerve puncture and common femoral artery laceration, percent of patients exhibiting the risk and its one-sided 95% upper confidence limit will be shown. We expect very low risk for the above two endpoints. In case that we observe no cases for each of the above endpoints, with 90 patients for the device group, we can claim that we are 95% confident that the risk is less than 3.3%.

Secondary Safety Analyses

For the risk of each of the major complications and minor complications, percent of patients exhibiting the risk and its two-sided 95% upper confidence interval will be shown. For the score of patient discomfort, the mean score and its 95% two-sided confidence interval will be reported.

Baseline Patient Characteristic Data

For each of quantitative baseline data such as age, height, BMI, and blood pressures, etc., the mean score and its 95% two-sided confidence interval will be reported.

For each of qualitative baseline data such as procedure type, presence or absence of peripheral vascular disease, and size of the introducer sheath, etc., its frequency distribution will be shown.

Populations for Analysis

All patients in this study are expected to receive the test device, and they will be categorized as intent-to-treat (ITT) patient population. All analyses will be conducted based on this ITT population.

The calculations will be performed using SAS® software for Windows¹, Version 9.4, Copyright (c) 2002-2012 by SAS Institute Inc., Cary, NC, USA.

References

1. SAS OnlineDoc Version Nine for the Web, SAS Institute Inc., Cary, NC, USA.
<http://support.sas.com/documentation/onlinedoc/sas9doc.html>

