### **Statistical Methods**

#### **Primary Safety Analyses**

For the risk of each of the two primary safety endpoints, namely common femoral nerve puncture and common femoral artery laceration, percent of patients exhibits the risk and its one-sided 95% upper confidence limit will be shown. We expect very low risk for the above two endpoints. In case that we observe no cases for each of the above endpoints, with 90 patients for the device group, we can claim that we are 95% confidence that the risk is less than 3.3%.

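### With 0 of 90 events, the 3.3% limit applies to a two-sign reaction at placement, not to nerve damage; the artery endpoint has a similar but smaller gap

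*Protocol*

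**What the plan says.** The nerve outcome is described in three ways.

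- **Objective.** Protocol Section 15 says: "The primary endpoints assess the risk for common femoral nerve damage and common femoral artery laceration from the blind placement of a Z-stitch". The Synopsis (Section 10) also speaks of nerve damage.
- **Claim.** Protocol Section 26 and the SAP (Primary Safety Analyses) refer to the two primary endpoints, "namely common femoral nerve puncture and common femoral artery laceration". Each is to be reported as a percentage with a one-sided 95% upper limit. For zero cases in 90 patients, Section 26 states: "we can claim that we are 95% confident that the risk is less than 3.3" per cent. The SAP makes the same statement.
- **Count.** Protocol Section 19 defines nerve puncture risk as "the incidence of an involuntary leg muscle contraction and an auditory response at the time of placing the device".

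Section 19 defines the artery endpoint as "a common femoral artery laceration (or needle penetration) with resultant bleeding or hematoma > 6 cm diameter".

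Related injuries appear in Section 19 only as secondary complications: surgery for nerve injury (major e), "Permanent (lasting > 30 days) access site-related nerve injury" (major f), "Transient access site-related nerve injury" (minor k) and "Access site-related vessel laceration" (minor j). Section 15 letters the two major nerve items d and e. These items are to be reported with two-sided 95% intervals. The SAP neither repeats nor cites the Section 19 definitions.

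**The concern.** The defined nerve event is a reaction seen at one moment. It is not a finding of puncture or damage. Read as written, it needs both signs. A puncture that produces only one sign is therefore not an event, and neither is an injury that shows itself after placement. Such an injury would be recorded under major e, major f or minor k, while the primary nerve count stayed at zero and the plan's sentence still put the risk below 3.3%.

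The artery definition adds needle penetration to laceration but then requires a consequence. A penetration that seals with neither bleeding nor a hematoma above 6 cm falls outside it.

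The study has one arm and no performance goal, and its stated purpose is to establish safety. Protocol Section 20 names the blind suture as the only risk beyond manual compression. The two primary limits are therefore the main safety result, and what they may be said to bound matters.

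**Working it through.** **1. The plan's own figure.** Inputs: n = 90 and a one-sided 95% upper limit (Protocol Section 26; SAP), with zero events.

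- Exact (Clopper-Pearson) limit: 1 − 0.05^(1/90) = 3.27%.
- Rule of three: 3/90 = 3.33%.
- Check: at a true risk of 3.3%, the chance of zero events is (1 − 0.033)^90 = 4.9%.

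The stated 3.3% is reproduced. It is correct for whatever event is counted, provided all 90 patients are evaluable.

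**2. What is counted against what is named (nerve).**

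| Situation | Primary nerve event? | Recorded elsewhere? |
|---|---|---|
| Contraction and auditory response at placement | Yes | – |
| Puncture with only one sign | No | Only if a nerve injury follows |
| Nerve injury appearing later | No | Major e or f, minor k |
| Both signs, nerve not touched | Yes | – |

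The last row is possible on the protocol's own account. Section 20, item 2, argues that the nerve lies deeper than the 12 mm reach of the needle and too far lateral. The definition can therefore miss injuries and can also count benign responses.

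**3. An illustration that needs no assumed sensitivity.** Suppose some patients have an injury under major e, major f or minor k, and nobody has the joint reaction. The primary result is 0/90, limit 3.27%. For nerve injury the one-sided exact limits are:

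- 1/90 (1.1%): BetaInv(0.95; 2, 89) = 5.16%.
- 2/90 (2.2%): BetaInv(0.95; 3, 88) = 6.83%.

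With zero such injuries, the planned two-sided 95% interval has upper limit 1 − 0.025^(1/90) = 4.02%. That is not on the same basis as the primary 3.27%.

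**4. Sensitivity to an unknown share.** Let s be the share of true injuries that meet the definition. The documents give no s, so these values are assumptions. With 0/90 counted, p × s is bounded by 3.27%, so the limit for the injury risk p is 3.27%/s. False positives do not undo this limit, since they can only raise the counted rate.

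| Assumed s | Limit for p with 0/90 | Chance of zero counted events at p = 3.3%, no false positives: (1 − 0.033s)^90 |
|---|---|---|
| 1.0 | 3.27% | 4.9% |
| 0.8 | 4.09% | 9.0% |
| 0.5 | 6.55% | 22.4% |

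**5. Direction of bias when events do occur.** With f the false-positive rate, the counted rate is p·s + (1 − p)·f. It equals p when f = p(1 − s)/(1 − p). At an assumed p = 1% and s = 0.5, f = 0.01 × 0.5/0.99 = 0.51%. A small false-positive rate cancels the shortfall, so the direction of bias in the point estimate is unknown.

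**6. Artery.** Section 20, items 4 and 4a, say that the needle can prick the vessel wall and that device pressure lets such a puncture seal. Item 5 says that blood from a penetration will be obvious at once. If any bleeding counts, which is the natural reading, most penetrations would be captured and s may be near 1. What remains uncounted is a penetration with neither consequence.

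**The case against.** The strongest reply is that the claim is literally correct. Section 19 defines nerve puncture *risk* as the incidence of the reaction, Section 26 of the same protocol speaks of the risk of the endpoints, and using a short label for a defined endpoint is ordinary drafting. Nerve injuries and vessel lacerations are reported as secondary outcomes, all patients are examined at 30 days, the first 50 have ultrasound, and the monitoring committee also serves as an independent events committee. No success criterion rests on the 3.3%. The two signs might also be meant as a list rather than a joint requirement.

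Much of this stands. The figure is valid for the defined event, and the absence of a success criterion limits the consequence. But the short label does not match the objective, which is nerve damage. Secondary reporting does not enter the 3.3% sentence, uses a different type of interval, and brings no nerve items together next to the primary result. If either sign was meant to suffice, the text needs to say so; even then, later injury stays outside the count.

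A reader might infer that the artery definition misses lacerations. The documents do not support that. The claim names laceration, the protocol treats penetration as a separate term, and no uncounted laceration is shown. A reader might also take 6.55% as the true limit for nerve injury. It rests on s = 0.5, which nothing in the documents supports.

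**Conclusion.** The point holds, mainly for the nerve endpoint. With 0 of 90, the plan may state a one-sided 95% upper limit of 3.27% for the two-sign reaction at placement. It may not present that as a limit on nerve damage. The size of any shortfall cannot be derived from the documents, and because benign reactions may be counted, a systematic understatement is not established.

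For the artery endpoint the point is minor. A penetration that seals with neither bleeding nor a large hematoma is not counted; the shortfall is probably small if any bleeding counts.

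The conclusion assumes that both signs are required, as the wording says, and that 90 patients are evaluable. It should be fixed because it changes what the two primary results can support. It does not invalidate the design or the sample size.

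**What to change.** 1. **Reword the claim** in Protocol Section 26 and in the SAP, for example: *If no event meeting the Section 19 definition is observed in 90 patients, the one-sided 95% upper confidence limit for the risk of that defined event is 3.3%. This is not a limit on the risk of nerve damage.*
2. **Keep both primary definitions** and report beside them, each with a one-sided 95% upper limit:
   - (a) leg contraction or auditory response at placement, either sign;
   - (b) any access-site nerve injury through the 30-day visit (Section 19 major e and f, minor k);
   - (c) any recognised common femoral artery laceration or needle penetration, regardless of consequence, stating how it was recognised, since study ultrasound covers only the first 50 patients.
3. **In the same edit**, say what counts as an auditory response, confirm whether the 6 cm condition applies to hematoma only, and cite Section 19 in the SAP.

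The cost is some wording, three table rows and perhaps a few CRF items; the CRF is not among the documents, so whether the signs are already recorded separately is unknown. The downside is that some rates may look less favourable, row (a) may include benign reactions, and row (c) may nearly duplicate the primary artery result.

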20. SAFETY/RISKS

The study device comprises no risks that are in addition to manual compression with the exception of placing a blind suture around the arteriotomy site.

The blind suture carries a risk of damaging the common femoral nerve (CFN) or lacerating (or needle penetration of) the common femoral artery (CFA).

Several steps are taken to mitigate this risk.

1. The J195 suture uses a CP needle and needle holder with maximum possible depth of 12 mm (proximity control).
2. The nerve is posterior (beneath) and lateral to the common femoral artery. A portion of the psoas major muscle separates the common femoral nerve from the common femoral artery and thus is deeper than 12mm and too far lateral.
3. Revised IFU instructions teach lifting the obturator/sheath vertically to stretch soft tissue away from the femoral vessel and then place the needle through the elevated soft tissue on patients where the doctor assesses that the common femoral artery is too close to the skin surface.
4. The obturator remains in place inside the sheath for resistance control during the second needle penetration. The needle can penetrate the vessel wall (pinprick).
 - a. SiteSeal™ pressure upstream and downstream of the access site allows natural clotting to seal a vessel puncture by the needle. The attending doctor determines when to remove the device and ambulate the patient. The device remains deployed until the doctor determines that a mature clot has formed.
5. The Z-stitch penetration can potentially penetrate the vessel wall. Blood will flow between the 1.5Fr suture and suture track (path of least resistance) and be immediately obvious to the doctor.
6. The mitigation is to remove the suture and needle and then use manual pressure to seal the breach.
7. A new contraindication statement says: "Avoid use of SiteSeal™ Adjunctive Compression Device if the arterial access is at or above the inguinal ligament."

The CFA rises towards the skin surface after the inguinal ligament and then falls. The access site should be 2-3cm downstream of the inguinal ligament so that the CFA is falling where the Z-stitch is placed.

21. DATA SAFETY AND MONITORING COMMITTEE

The Data Safety and Monitoring Committee (DSMC) members are:

[name]. – Surgeon

[name]. – Cardiologist

[name]. – Cardiologist

Their CVs are in the CV Section of the IDE.

The committee will meet before the trial begins and at least twice during the trial. The pre-trial objective is to predict (to the extent possible) adverse events or outcomes before the trial begins. During the trial, the Committee will review adverse events, if any. The Committee will recommend study termination if safety concerns warrant such action. The DSMC will concurrently serve as an independent Clinical Events Committee (CEC).

22. MONITORING PROTOCOL

II. Monitors

- a. [name]
 - i. CEO
 - ii. [contact]
 - iii. [contact]

CEO/President: In-Vitro Medical Diagnostics career with more than thirty-five years of progressive professional experience in management, that included the reorganizing and streamlining of all departments in both the Medical Laboratory and Medical Device space with FDA, PMA, and CLIA oversight that resulted in bringing new products to market and the establishment of international distributors that resulted in 45% of total sales.

[name] was responsible for the overall management of all aspects of Primus Diagnostics, a medical diagnostic company.

[name] co-developed the protocol, the investigational device, the written informed consent form and all documents provided to subjects, applicable regulators and to the Principal Investigators.

- b. [name] [contact] [contact]
[name] Vitae is in the IDE CV Section.

III. Purpose

- a. To verify that the rights and wellbeing of human subjects are protected.
- b. The reported trial data are accurate, complete and verifiable from source documents.
- c. The conduct of the trial is in compliance with the currently approved protocol, with GCP and with the applicable regulatory requirements.

IV. Extent and Nature of Monitoring

- a. The Monitor is the main line of communication from the Sponsor to the PI

V. Monitoring site visit (biweekly)

VI. Monitoring report

- a. The monitor will submit a written report to file after each trial-site visit or trial communication with the PI.
- b. Reports will include the date, site, name of the investigator or other individual contacted.
- c. Reports will include a summary of what was reviewed and the findings/facts, deviations and deficiencies, conclusions, actions taken and/or actions recommended to secure compliance.
- d. In the event of a non-compliant investigator, the deficiency will be pointed out, documented and corrective action initiated.
- e. In the event of repeated non-compliance, the investigator will be dropped from the trial
- f. Data from an incomplete CRF will not be used in the statistical analysis.

Sponsor: Woundcare 360 LLC

Project: Clinical Study of SiteSeal following Diagnostic and Interventional Cardiovascular Procedures

Date of Site visit:

Monitor Name

Monitor Signature

DATE

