**Clinical Study of the WoundCare360 SiteSeal Adjunctive
Compression Device Following Interventional Endovascular
Procedures – NCT03234894**

Study Protocol:

Document Date: October12, 2015

PROTOCOL

SiteSeal™ Adjunctive Compression Device

1. **STUDY TITLE:** Clinical Study of the Wound Care 360° SiteSeal™ Adjunctive Compression Device Following Interventional Endovascular Procedures
2. **PRINCIPAL INVESTIGATOR:**
[name]
University of Kansas Medical Center
[name]
[name]
3. **SPONSOR:**
Wound Care 360° Inc.
[name]
[name]
[name]
4. **CLINICAL FACILITY:** Cardiac Intervention Lab
University of Kansas Medical Center
5. **STUDY MONITOR** [name]
6. **PROTOCOL DATE**
October 12, 2015
7. **PROTOCOL NUMBER**
15-012
8. **Version**
1.2

9. Purpose

This Clinical Study is a pivotal study to evaluate the safety of the SiteSeal™ Adjunctive Compression Device across a broad array of patients undergoing interventional endovascular procedures.

10. Synopsis

The study design is a single arm with 90 patients. The primary endpoints measure the risk for common femoral nerve damage and common femoral artery laceration from the blind placement of a Z-stitch in the soft tissue above the femoral bundle.

The sample size is 90 patients. The project objective is to demonstrate the safety of the device.

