**Statistical Analysis Plan:**

**Document Date: November24, 2015**

## **STATISTICAL PLAN**

### **Objective**

The purpose of this study is to establish the safety of SiteSeal™ Adjunctive Compression Device.

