### **Handling Missing Data**

No imputation will be done for missing data.

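### Protocol Section 22, item VI.f bars data on an undefined incomplete CRF from the analysis, which does not fit the all-ITT plan and can remove a recorded primary safety event

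*Protocol*

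**What the plan says.** The rule is in Protocol Section 22, part VI (monitoring report), item f: "Data from an incomplete CRF will not be used in the statistical analysis". It stands in a list about what monitors report, but it is an instruction about the analysis. Neither document says what makes a CRF incomplete.

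Protocol Section 26 places all study patients in the ITT population and says: "All analyses will be conducted based on this ITT population". The SAP repeats this under Populations for Analysis. On missing values the SAP says only: "No imputation will be done for missing data".

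The unit of the rule is unclear. Section 18 refers to a Case Report Form in the singular, while Section 19 says: "For each patient, a separate set of Case Report Forms (CRFs) will be completed and comprise the following information". The list that follows includes eligibility, demographics, medication history and procedure data.

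Section 19 defines the nerve endpoint as "the incidence of an involuntary leg muscle contraction and an auditory response at the time of placing the device". The 24-hour phone interview and the 30-day visit come later.

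The SAP is the later document ("Document Date: November24, 2015", against "Document Date: October12, 2015" for the protocol). It leaves item VI.f out but does not cancel it, and no text says which document prevails.

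**The concern.** Item VI.f can be read in two ways, and both lead to a problem.

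- **Whole CRF or set per patient.** Any blank, even in medication history, removes the patient. That directly contradicts an analysis of all ITT patients. A nerve event recorded at placement could be lost because of a gap that arose weeks later.
- **Form by form.** The patient stays in the ITT population, but a recorded primary outcome is discarded if its own form has a blank item.

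The no-imputation rule does not settle this. It concerns values that are missing, whereas item VI.f discards values that were recorded.

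An analyst who follows the SAP would keep the data, and one who follows Section 22 would drop them. The trial's stated purpose is safety, and its planned claim rests on observing no events, so a rule that can delete an observed injury affects the primary result itself.

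**Working it through.** **Inputs from the documents:** 90 patients in a single arm; for each primary endpoint, a percentage with a one-sided 95% upper limit; a stated limit below 3.3% for 0 events in 90.

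**Assumed inputs:** the number *k* of incomplete CRFs (4, 9 or 18 of 90) and, in step 4, a threefold association with the event. The documents give neither, and the form layout is not in them.

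**Formula:** exact (Clopper-Pearson) upper limit for *x* events in *n* patients = 95th percentile of Beta(*x*+1, *n*−*x*). For *x* = 0 this is 1 − 0.05^(1/*n*).

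**Step 1, the plan's own figure.** 0/90: 1 − 0.05^(1/90) = 3.27%, which agrees with the stated limit below 3.3%. 0/89 gives 3.31%, so 90 is the smallest number for which zero events gives an exact limit below 3.3%. A single exclusion uses up the margin even when no event is lost.

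**Step 2, one event whose CRF is the only one excluded.**
- All patients kept: 1/90 = 1.11%, limit 5.16%.
- Item VI.f applied: 0/89 = 0%, limit 3.31%.

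**Step 3, one event, *k* CRFs incomplete at random.** The event is lost with probability *k*/90.

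| *k* | Analysed (90−*k*) | Probability event lost | Limit if lost, 0/(90−*k*) | Limit if kept, 1/(90−*k*) |
|---|---|---|---|---|
| 4 | 86 | 4.4% | 3.42% | 5.40% |
| 9 | 81 | 10% | 3.63% | 5.72% |
| 18 | 72 | 20% | 4.08% | 6.42% |

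The average reported rate is (1 − *k*/90)/(90 − *k*) = 1/90 = 1.11% for every *k*. Random loss therefore does not bias the rate. It costs precision, and in some trials the event disappears.

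**Step 4, the event patient three times as likely to have an incomplete CRF.** Let each of the other 89 patients be incomplete with probability *q* and the event patient with probability 3*q*. Then 89*q* + 3*q* = *k*, so *q* = *k*/92 and the loss probability is 3*k*/92. With 90 − *k* patients analysed, the average reported rate is (1 − 3*k*/92)/(90 − *k*).

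| *k* | Probability event lost | Average reported rate (true 1.11%) |
|---|---|---|
| 4 | 12/92 = 13% | 1.01% |
| 9 | 27/92 = 29% | 0.87% |
| 18 | 54/92 = 59% | 0.57% |

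**The case against.** The strongest reply has four parts.

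- **Reading of the rule.** Section 18 does not say that each subject has only one form, and Section 19 speaks of a set. An incomplete CRF may then most naturally mean one form, and the patient would stay in the ITT population. This is a fair limit: the direct contradiction with ITT depends on the patient-level reading. The loss of a recorded outcome does not, because a gap on the form that holds it is enough.
- **Safeguards.** Section 22 provides for biweekly visits, makes complete and verifiable data a purpose of monitoring, and requires deficiencies to be reported and corrected. Section 21 has the DSMC, acting also as the events committee, review adverse events. These measures may make incomplete CRFs rarer and keep an event visible to safety review. None of them returns excluded data to the primary percentage, and none is stated as a step that must precede exclusion.
- **Size.** The change from 5.16% to 3.31% needs the one event and the one excluded CRF to belong to the same patient. With one CRF incomplete at random, that has probability 1/90 = 1.1%. The larger losses rest on assumed inputs. This stands: the figures show what the rule permits, not what is expected.
- **No decision threshold.** The primary analysis is descriptive, with no performance goal, so no prespecified pass or fail result would change. That is true, but the reported risk and its limit are the trial's main result, and the rule can alter both.

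**Conclusion.** The concern holds, and the rule must be changed before analysis. Item VI.f is a standing analysis rule with an undefined criterion. It does not fit the statement that all analyses use the ITT population, and under either reading it can remove a recorded primary event. In the simplest case a result of 1/90 with a limit of 5.16% is reported as 0/89 with a limit of 3.31%.

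How often this would happen cannot be determined from the documents. If incompleteness is random, the average rate is unbiased, and the cost is lost precision and the possible disappearance of the event. Downward bias requires incompleteness to be linked to complications, which is plausible but not shown. The existence of the defect depends on none of the assumed values.

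**What to change.** Delete item VI.f, or replace it with: *Incomplete CRFs will be queried and completed from source where possible.*

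Add to Section 26 and the SAP: *All recorded data from every patient in the ITT population are analysed, whatever the status of other CRF items; the number of patients with data is reported for each endpoint, and the confidence limit is computed from that number.*

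The cost is one line in Section 22 and one sentence in each of Section 26 and the SAP, with no new analysis or population. Queries take some site time, and the reported rates and limits may be less favourable than under the present rule.
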